- Evaluate the complexity of cardiac surgery residents' learning curve for grafts quality assessment with HFUS as isolated technique.
- Evaluate the complexity of cardiac surgery residents' learning curve for grafts quality assessment with TTFM as isolated technique.

STUDY DESIGN AND DURATION

This is a prospective, observational, monocentric cohort study in which adult patients undergoing coronary artery bypass surgery will be enrolled.

The study will last four months: three months for patients enrollment and data collection and one month for statistical analysis and scientific paper writing.

The trial will start after obtaining favourable opinion from the local Ethics Committee and could be considered completed when all the eight cardiac surgery residents involved have reached primary endpoint.

INCLUSION CRITERIA

- Age ≥ 18 years old;
- Written informed consent;
- Indication to CABG surgery (both «on-pump» and «off-pump»);
- Stable angina, unstable angina or acute coronary syndrome without ST elevation (NSTEMI).

EXCLUSION CRITERIA

- Age ≥ 18 years old;
- Written informed consent;
- Indication to CABG surgery (both «on-pump» and «off-pump»);
- Stable angina, unstable angina or acute coronary syndrome without ST elevation (NSTEMI).

STUDY PROCEDURES

All patients with coronary artery disease and an indication for surgical revascularization (coronary artery bypass grafting) who meet the above-described inclusion and exclusion criteria will be enrolled by signing the informed consent the day before surgery.

Patient data (anamnestic data, surgery description, *intraoperative echographic and flowmetric measurements*) will be recorded in a dedicated database. All data recorded in the database are commonly acquired for all patients undergoing this type of surgery and no further examinations will be performed for patients included in the trial.

The study will involve cardiac surgery residents with different levels of training and an expert cardiac surgeon who acts as supervisor and benchmark. Each resident will sign a dedicated informed consent form in the presence of a doctor foreign to the study protocol (Cardiac Surgery ward cardiologist). The residents will be “blinded” about the trial objective and the adopted score system. They will undergo a specific training including a quick lesson and a practical workshop to familiarize with the equipment.

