During surgery, every graft will be evaluated through transit time flowmetry (TTFM) and intraoperative ultrasound control (HFUS).

In details, the ultrasound control is carried out through a dedicated sterile ultrasound probe connected to a machine (MiraQ - MEDISTIM) as soon as each anastomosis is completed. The result of the evaluation is recorded together with surgery data. This evaluation is intended to confirm the correct realization of the anastomosis and provides a proof of its patency.

Once each graft is completed, the resident will be given 60 seconds to acquire two HFUS recordings (short and long axis). After that, the supervisor will perform his personal recording which will stand as benchmark. The following items will be evaluated:

- A) Long axis recording acquired within 60 seconds [YES → 1] [NO → 0]
- B) Long axis recording judged as suitable by the supervisor [YES → 1] [NO → 0]
- C) Short axis recording acquired within 60 seconds [YES → 1] [NO → 0]
- D) Short axis recording judged as suitable by the supervisor [YES → 1] [NO → 0]

E) Correct interpretation of the anastomosis as adequate or inadequate [YES → no penalty] [NO → total score becomes 0 and the resident isn't allowed to perform TTFM]

Each resident will be given a HFUS-related score from a minimum of 0 to a maximum of 4. Whenever one of the recordings will be judged as non-suitable by the supervisor and consequently useless for a correct interpretation of the anastomosis (score 0 for items A and/or C), item E won't be evaluated and the HFUS will be given a total score of 0.

Next step will be the TFM evaluation, which is carried out through a specific sterile device connected to the same machine (MiraQ - MEDISTIM) once the patient has been weaned from the cardiopulmonary bypass and before protamine administration. This recording is performed under EKG and pressure-controlled conditions. Although there is no general agreement on the optimal mean arterial pressure at which the measurement has to be recorded, we will adopt the standard used in the REQUEST study protocol (16), that is an average pressure of 80 mmHg.

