The resident will acquire the TTFM recording after each graft is completed. To make the comparison as accurate as possible, the resident will perform TTFM evaluation on one graft at a time and successively the supervisor will do the same for each graft (making sure that delta between the pressure during the two recordings is lower than 10 percent and that no drug has been administered). The following items will be evaluated:

F) Time necessary to acquire the measures [$< 30 \text{ sec} \rightarrow 1$] [$> 30 \text{ sec}, < 60 \rightarrow 0.5$] [$> 60 \text{ sec} \rightarrow 0$]

G) Need for multiple measurements before the final one: [$> 2 \rightarrow 0$] [$1 \rightarrow 0.5$] [$0 \rightarrow 1$]

H) Need to change probe dimensions: [NO $\rightarrow 0$] [YES $\rightarrow 1$]

I) ACI [delta between resident and supervisor measurements $< 10\% \rightarrow 1$] [$> 10\%, < 20\% \rightarrow 0.5$] [$> 20\% \rightarrow 0$]

L) Mean Flow [delta between resident and supervisor measurements $< 10\% \rightarrow 1$] [$> 10\%, < 20\% \rightarrow 0.5$] [$> 20\% \rightarrow 0$]

M) Pulsatility Index [delta between resident and supervisor measurements $< 10\% \rightarrow 1$] [$> 10\%, < 20\% \rightarrow 0.5$] [$> 20\% \rightarrow 0$]

N) Backward Flow [delta between resident and supervisor measurements $< 10\% \rightarrow 1$] [$> 10\%, < 20\% \rightarrow 0.5$] [$> 20\% \rightarrow 0$]

O) Diastolic Filling [delta between resident and supervisor measurements $< 10\% \rightarrow 1$] [$> 10\%, < 20\% \rightarrow 0.5$] [$> 20\% \rightarrow 0$]

P) Correct interpretation of the graft quality as working [YES \rightarrow no penalty] [NO \rightarrow total score becomes 0]

Each resident will be given a TTFM-related score from a minimum of 0 to a maximum of 8.

The final score for each graft will be the sum of the two scores (HFUS and TTFM), from a minimum of 0 to a maximum of 12.

The same procedure will be repeated for each graft performed during the surgery.

Each resident will continue until reaching a ratio between total score and number of evaluated anastomoses of 11.

END-POINTS

Primary end-point

Number of anastomoses needed to reach a ratio (total score/n. of anastomoses) ≥ 11

Secondary end-points

- Number of anastomoses needed to reach a ratio (HFUS score/n. of anastomoses) = 4
- Number of anastomoses needed to reach a ratio (TTFM score/n. of anastomoses) ≥ 7

STATISTICAL ANALYSIS AND SAMPLE SIZE CALCULATION

Sample size calculation

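### As a running mean, the HFUS endpoint (ratio = 4) can be met only at graft 1 or never, and the primary ratio ≥ 11 mixes early losses with time to competence

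*Combined protocol and SAP*

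**What the plan says.** STUDY PROCEDURES scores each graft from 0 to 4 for HFUS ("Each resident will be given a HFUS-related score from a minimum of 0 to a maximum of 4"), from 0 to 8 for TTFM, and from 0 to 12 in total. If a recording is unsuitable, "the HFUS will be given a total score of 0". A wrong interpretation at item E also zeroes the score, and TTFM is then not done on that graft.

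The three endpoints under END-POINTS are:

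- primary: "Number of anastomoses needed to reach a ratio (total score/n. of anastomoses) ≥ 11"
- secondary, HFUS: "Number of anastomoses needed to reach a ratio (HFUS score/n. of anastomoses) = 4"
- secondary, TTFM: "Number of anastomoses needed to reach a ratio (TTFM score/n. of anastomoses) ≥ 7"

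The stopping sentence in STUDY PROCEDURES reads "Each resident will continue until reaching a ratio between total score and number of evaluated anastomoses of 11". No window, reset, minimum number of grafts or censoring rule is given. STUDY DESIGN AND DURATION treats the study as complete once all eight residents have met the primary endpoint. A secondary objective concerns the "learning curve for grafts quality assessment with HFUS as isolated technique".

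**The concern.** The HFUS target equals the HFUS maximum. On a running mean, one imperfect graft can never be made up, so a resident who starts badly and becomes excellent is recorded the same way as one who never improves. The Background itself expects the basics of HFUS to take about 10–20 grafts. A resident who follows that course is recorded as never reaching the endpoint.

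The primary and TTFM targets lie 1 point below their maxima. Early losses can be repaid, but only slowly, so the count reflects how bad the early grafts were as well as when competence began. A resident who settles at a steady 11 after any earlier loss never reaches the primary endpoint, although completion of the study depends on all eight doing so. At the other extreme, a first graft of 11 or 12 ends the series at n = 1.

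**Working it through.** **Inputs.** From STUDY PROCEDURES: maxima of 4 (HFUS), 8 (TTFM) and 12 (total). From END-POINTS: targets of 4, 7 and 11. From the sample size section: 8 residents, about 10 surgeries each, 4 patients per week, 3 months. The early and plateau scores used below are illustrations, because the plan gives no expected scores.

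**The plan's own figure.** 8 × 10 = 80 patients, as stated. At 4 per week, 12–13 weeks yield 48–52 patients, or 6–6.5 surgeries per resident instead of 10. Assuming 2–4 anastomoses per surgery, a resident sees 20–40 grafts as planned (10 × 2 to 10 × 4), or 12–26 at the stated accrual (6 × 2 to 6.5 × 4).

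**HFUS.** With each score at most 4, the sum over n grafts equals 4n only if all n scores are 4. If that holds at any n, it already held at n = 1. Enumerating all 5^6 = 15,625 sequences of six scores from 0 to 4 confirms it: 3,125 reach the target at graft 1, 12,500 never do, and no other value occurs. If p is the chance of a perfect first graft (assumed, independent between residents), a resident never reaches the endpoint with probability 1 − p, and all eight reach it with probability p^8. At p = 0.5 these are 50% and 0.4%; at p = 0.8 they are 20% and 17%.

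**Primary.** Suppose the first m grafts score s and later grafts score b > 11. The deficit is m(11 − s) and each later graft repays b − 11, so the target is met at n = m + m(11 − s)/(b − 11).

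| m | s | b | n |
|---|---|---|---|
| 10 | 8 | 11.5 | 10 + 30/0.5 = 70 |
| 10 | 10 | 11.5 | 10 + 10/0.5 = 30 |
| 5 | 8 | 11.5 | 5 + 15/0.5 = 35 |
| 20 | 8 | 11.5 | 20 + 60/0.5 = 140 |
| 10 | 8 | 12 | 10 + 30/1 = 40 |
| 10 | 10 | 12 | 10 + 10/1 = 20 |
| 3 | 0 | 12 | 3 + 33/1 = 36 |
| 10 | 8 | 11 | never |

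The count does rise with a longer poor phase (35, 70, 140), so it carries information. It can also reverse the order of two residents. Three zeros then 12s gives 36, while ten 10s then 12s gives 20, although the first resident is competent from graft 4 and the second from graft 11.

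In general, k whole-graft zeros followed by perfect grafts give n = k + 11k = 12k. The milder miss of HFUS 0 with TTFM 8 (total 8) gives n = k + 3k = 4k.

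**TTFM.** A graft gains at most 1 on the target of 7 and loses up to 7, so k zeros then perfect grafts give n = k + 7k = 8k.

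**Item H** ("Need to change probe dimensions"). As printed, it gives 0 when no change is needed. Such a graft cannot exceed 7 for TTFM or 11 in total, so it never repays a deficit. If that is intended, a resident who never changes probe meets the primary and TTFM endpoints at graft 1 or never.

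**Last-five mean, for comparison.** With j of the five grafts at 11.5 and the rest at 8, the sum is 40 + 3.5j ≥ 55, so j = 5 and the target is met at graft 15. With the rest at 10, the sum is 50 + 1.5j ≥ 55, so j = 4 and it is met at graft 14. The reversed pair above becomes graft 8 (three zeros) and graft 13 (ten 10s), in the order in which competence began.

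**The case against.** The strongest objection concerns the reading. The text never says cumulative, items E and P use the term total score for a single graft, the stopping sentence follows one about repeating the procedure within a surgery, and the sample size is planned in surgeries. On a per-operation ratio, HFUS = 4 would mean one operation with every graft perfect, which can happen at any stage. That the running mean gives an absurd result is some evidence that it was not meant. This stands as a qualification. Yet the per-operation rule is written nowhere, and the stopping sentence divides by the number of evaluated anastomoses. On either reading the denominator needs defining.

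Second, a cumulative mean that penalises early errors is a strict but legitimate choice for the primary endpoint, and the contrast of 70 with 30 relies on a plateau just above target (40 and 20 at a plateau of 12). This also stands. The primary and TTFM changes are improvements; the HFUS endpoint is what fails.

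Third, HFUS is scored on every graft, so a curve could still be drawn. True, but the stated endpoint would not summarise it, and stopping on the total ratio can cut the HFUS series short.

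Finally, read literally, the zeroing rule makes HFUS almost always 0 or 4, so many enumerated sequences could not occur. The conclusion is the same.

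**Conclusion.** The point holds, conditional on the running-mean reading that the stopping sentence favours. For HFUS the result is exact and needs no assumed scores: with no minimum number of grafts, the only possible values are 1 and never. Following the rule as written would leave the isolated-HFUS objective without a usable result, so it must be fixed.

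For the primary and TTFM endpoints the fault is one of interpretation and attainability. The counts are informative but mix two quantities, and values such as 70 or 140 lie beyond the 12–40 grafts a resident is likely to see (assuming 2–4 anastomoses per surgery). The Statistical analysis section has no method for a resident who never reaches a target. How often real residents would be affected cannot be derived from the documents.

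**What to change.** Before data collection, define the endpoints on a moving window, for example five consecutive evaluated anastomoses:

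- **Primary:** first anastomosis at which the mean total score of the last 5 is ≥ 11.
- **HFUS:** first at which the last 5 HFUS scores are all 4.
- **TTFM:** first at which the mean of the last 5 TTFM scores is ≥ 7.

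End a resident's series when the primary and HFUS criteria have both been met or enrolment closes. Both are needed, because the primary alone can be met with one HFUS zero in the window: (8 + 4 × 12)/5 = 11.2. TTFM then follows, since a mean total ≥ 11 with HFUS ≤ 4 implies TTFM ≥ 7. Censor a resident who has not met a criterion at the last scored anastomosis. Report how many of the 8 met it and a Kaplan-Meier median, which may not be reached with so few residents. Keep the cumulative ratio as a descriptive curve.

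Confirm the direction of item H before fixing the 11 and 7 targets. State how a graft without TTFM counts in the TTFM series. Align the completion sentence in STUDY DESIGN AND DURATION. If a per-operation ratio was intended, write that instead.

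The cost is the wording of three endpoints, the stopping and completion sentences, and short lines on censoring and on grafts without TTFM. The score sheet is unchanged. Some residents will score more grafts than now, within planned enrolment; none can finish before graft 5; and the window length is a convention. Chance runs remain possible: with a constant, independent 50% chance of a 4 (assumption), five in a row occurs in 3% at graft 5 (0.5^5) and 25% by graft 20, against 50% at graft 1 under the present wording.

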Furthermore, surgeons must overcome a learning curve to handle both techniques properly, but few data are available according the current literature. The ability of mastering TTFM and HFUS comes gradually but incessantly; constant learning and self-assessment make surgeons continuously improve (9).

Regarding TTFM, when correctly applied it can provide invaluable information about graft flow; however, proper handling technique is paramount. (6) A learning curve is required to interpret it correctly and, in particular at the beginning, diagnostic errors and unnecessary graft revision cannot be excluded. (8)

The basics of TTFM are easy to learn, while the nuances come gradually but constantly; with continued routine use, one begins to appreciate subtle changes of coronary flow in order to detect flow competition or the difference between a perfect graft and a less-than-perfect but functioning one. (9, 10). In light of this, some authors suggest starting first with use of TTFM, use on every graft at least 4 times/graft and continue with this modality alone for at least 6 months. (9)

Instead learning to master the HFUS presents bigger technical challenges. Performing ultrasound on a moving target can actually be more difficult than performing the anastomosis itself, due to the need of maintaining stable and optimal acoustic contact between the ultrasound probe and the target without distorting the anastomosis. (9, 11, 12)

Detractors of this technique have highlighted as its major limit the lack of standardization because of its operator dependency. (13) Some authors though compared two experienced surgeons letting them observe and independently evaluate 120 consecutive anastomoses; having obtained identical results, they proved how, in experienced hands, epicardial ultrasound evaluation appears reproducible and operator independent. (14) Therefore, in order to gain experience, it is mandatory to apply HFUS routinely, starting with selected patients and after proper training from peers or radiologists. (13, 15) Despite HFUS learning curve requires more patience and attention to detail that TTFM, the basics can be learned in about 10–20 grafts. (9, 10)

STUDY OBJECTIVES

Primary objective

Evaluate the complexity of cardiac surgery residents' learning curve for grafts quality assessment with TTFM and HFUS.

Secondary objectives

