Our cardiac surgery unit performs between 5 and 10 coronary artery bypass grafts surgeries per week on average. Considering the inclusion and exclusion criteria and assuming that some patient may not give their informed consent, we expect to enroll 4 patients per week. Considering that the involved residents (8 in total) will take part to the procedures in turn and that we estimate around 10 surgeries to become autonomous, we estimate to enroll 80 patients during a period of 3 months.

Statistical analysis

Data will be collected in a specific database (Microsoft Excel worksheet). The Kolgomorov-Smirnov test was used to check for variables distribution. Continuous variables with a normal distribution are summarized by mean and standard deviation. Continuous variables with a non-normal distribution are expressed with median and interquartile range.

Categorical variables are reported as absolute frequency distribution and percentage. Continuous data are analyzed using the unpaired t-test or the Mann – Whitney test according to their distribution. Categorical data are compared with the Fisher's exact test. Statistical findings were considered significant if p value was less than 0.05. Statistical analysis will be performed with the statistic software SPSS (IBM).

BIBLIOGRAPHY

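### The planned enrolment rate, period and total do not fit together: 4 patients per week for three months gives 48-52 patients, not 80

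*Combined protocol and SAP*

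**What the plan says.** The Sample size calculation starts from a unit volume of 5 to 10 bypass operations per week. After allowing for the entry criteria and for patients who decline, it concludes: "we expect to enroll 4 patients per week". It then turns to the eight residents, who "will take part to the procedures in turn and that we estimate around 10 surgeries to become autonomous", and ends: "we estimate to enroll 80 patients during a period of 3 months".

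Study Design and Duration repeats the period: "The study will last four months: three months for patients enrollment and data collection" "and one month for statistical analysis and scientific paper writing". The same section says the trial "could be considered completed when all the eight cardiac surgery residents involved have reached primary endpoint". Study Procedures adds: "Each resident will continue until reaching a ratio between total score and number of evaluated anastomoses of 11".

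**The concern.** The rate, the period and the total stand in one short paragraph, and the rate multiplied by the period does not give the total. That paragraph is the plan's only justification of size and feasibility, and its three-month period reappears as the enrolment part of the stated study duration.

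What is at stake is the planned timetable and the planned number of patients. On the plan's own inputs, a typical resident would have had clearly fewer than the expected 10 or so operations when the three months ended. Anyone relying on the stated duration or the stated number, such as the ethics committee or the unit's own planners, is relying on figures that cannot all hold.

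**Working it through.** **Inputs, all from the documents**
- Enrolment rate: 4 patients per week, net of eligibility and consent losses (Sample size calculation).
- Residents: 8, taking turns (Sample size calculation).
- Surgeries per resident: about 10 (Sample size calculation).
- Enrolment period: 3 months (Sample size calculation; Study Design and Duration). I take this as 12 to 13 weeks; a calendar quarter is 13.04 weeks.
- Analysis and writing: 1 month, for a stated total of 4 months (Study Design and Duration).

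**Step 1. Where the 80 comes from.** Residents × surgeries = 8 × 10 = 80. The plan's figure is reproduced exactly, with one resident per operation.

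**Step 2. What the stated rate delivers in the stated period.** Rate × weeks:
- 4 × 12 = 48
- 4 × 13 = 52

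The shortfall is 80 − 52 = 28 (28/80 = 35%) to 80 − 48 = 32 (32/80 = 40%). The 80 is not reproduced.

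**Step 3. Per resident, if operations are shared equally.** 48/8 = 6 to 52/8 = 6.5 surgeries, against about 10.

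**Step 4. Time needed for 80 at the stated rate.** 80/4 = 20 weeks. With 365.25/12/7 = 4.35 weeks per month, 20/4.35 = 4.6 months. Adding one month for analysis and writing gives about 5.6 months, against the stated 4.

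**Step 5. Rate needed for 80 in three months.** 80/13 = 6.2 to 80/12 = 6.7 enrolled per week.

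**Step 6. Do other readings close the gap?**
- Enrolling through all four months (17.4 weeks), with no time left for analysis: 4 × 17.4 = 69.6. Still short of 80.
- Enrolling every patient at the lower end of the unit's volume: 5 × 12 = 60 to 5 × 13 = 65. Still short.
- At the upper end of the volume, 10 per week, the required rate is 6.2/10 = 62% to 6.7/10 = 67% of all operations. That is possible in principle, but it is not the rate the plan states.

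**The case against.** The strongest reply is that these are planning estimates, worded as such, and that nothing in the analysis depends on them. The study ends when all eight residents reach the threshold and each resident continues until then, so the calendar figures would give way in practice. Much of this stands. The consequence is limited to the planned timetable and total; what is measured and how it is analysed do not change. However, a gap of 35-40% is too large for rounding. Study Design and Duration also states four months flatly, while its completion rule is worded only as something that could apply.

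A second reply is that the unit does up to 10 operations per week, so 6.2-6.7 enrolled per week is attainable. This also stands in part: the rate of 4 may be the wrong input, and the documents do not show which of the three figures is wrong. The gross volume does not remove the conflict, though, because the 4 is given after losses have been allowed for.

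A reader might infer three stronger things, none of which the documents support:
- *The 80 is a miscalculation.* It is not; it equals 8 × 10. Equally, this does not show that 80 is adequate, since no basis is given for about 10 surgeries per resident.
- *The study is underpowered.* The plan states no power, effect size or precision that rests on 80.
- *The primary endpoint is biased because residents will be cut off at three months.* No section says enrolment closes at three months regardless of progress, and Study Procedures says the opposite.

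**Conclusion.** The point holds as an internal contradiction. A rate of 4 per week, a period of three months and a total of 80 cannot all be true, so at least one is wrong. The stated rate gives 48-52 patients, or 6-6.5 operations per resident. For 80, it implies 20 weeks of enrolment and about 5.6 months overall.

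The result rests on reading three months as 12-13 weeks and the weekly rate as constant and net, as the plan presents it. The per-resident figures also assume equal sharing. The 20 weeks is what the plan's inputs imply, not a forecast: actual enrolment depends on when the eighth resident reaches the threshold and may be shorter or longer. The arithmetic is certain. The effect is confined to the stated timetable and number, and the matter should be corrected because the correction is simple.

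**What to change.** Reconcile the three figures in the Sample size calculation and in Study Design and Duration, in one of these ways:
1. Keep the rate and the 80, and restate enrolment as about 20 weeks and the total as about 5.6 months.
2. Keep the rate and the three months, and restate the expected number as 48-52. The text should then acknowledge 6-6.5 operations per resident instead of about 10.
3. Correct the weekly rate and justify it. For 80 in three months it must be about 6.2-6.7 enrolled per week after eligibility and consent losses.

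In addition, make the existing completion rule firm. Study Design and Duration should say that the study ends when all eight residents have reached the primary endpoint, and that the duration in months is an estimate which gives way to that rule.

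The cost is a few words in two sections. The downside is a longer stated duration (about 1.6 months more under the first option) or a smaller stated number (under the second). The endpoint, the scoring and the completion rule itself do not change.
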